	7.1 7.2 7.3 7.4 7.5 7.6 7.7 7.8 7.9 7.10	PARTICIPANT RECRUITMENT MOBILE STUDY ACTIVITIES: MOSIO FOR RESEARCH ECG MONITOR: ZIO® XT PATCH EVENT MONITOR HOME SLEEP APNEA TEST TEXT MESSAGING SERVICE ENROLLMENT VISIT (PRE-SCREENING/PRE-CONSENT) BASELINE VISIT (BEFORE DAY 1) RANDOMIZATION AND MONITORING (DAY 1-14) ASSESSMENT OF SLEEP QUALITY MONITORING CLOSE-OUT VISIT (DAY 15+)	11 12 12 12 13
8	RIS	K AND BENEFIT ASSESSMENT	. 14
	8.1 8.2 8.3	RISKS BENEFITS ASSESSMENT OF POTENTIAL RISKS AND BENEFITS	14
9	DIS	CONTINUATION AND REPLACEMENT OF PARTICIPANTS	. 15
	9.1 9.2 9.3	EARLY DISCONTINUATION FROM RANDOMIZATION. WITHDRAWAL OF PARTICIPANTS FROM THE STUDY. REPLACEMENT OF PARTICIPANTS	16
10	STA	ATISTICAL METHODS AND CONSIDERATIONS	. 16
	10.1 10.2	SAMPLE SIZE AND RANDOMIZATION	

Disrui	oted	Sleep	and	Concurrent	Ectopy or	Atrial	Fibrillation

10.3	Intention-to-Treat (ITT)	16
11 AD	MINISTRATIVE, ETHICAL, REGULATORY CONSIDERATIONS	17
11.1	PROTOCOL AMENDMENTS	17
11.2	Informed Consent Form	17
12 DE	EEDENCES	47

Version Date: 03 June 2025

LIST OF ABBREVIATIONS

AF atrial fibrillation

CFR Code of Federal Regulations

ECG electrocardiogram

HGNS Hypoglossal nerve stimulation
 IEC Independent Ethics Committee
 IRB Institutional Review Board
 PACs Premature atrial contractions

PVCs Premature ventricular contractions

PROTOCOL SYNOPSIS

TITLE	Disrupted Sleep and Concurrent Ectopy or Atrial Fibrillation (DISCRETE AF)				
SPONSOR	Investigator-initiated				
FUNDING ORGANIZATION	UCSF Cardiology and the Heart Rhythm Society				
NUMBER OF SITES	1				
RATIONALE	To examine, in a randomized fashion to allow inference of causal effects, the acute relationship between sleep disruption and atrial and ventricular ectopy.				
STUDY DESIGN	This is a prospective, randomized, case-crossover study.				
GENERAL OBJECTIVE	To assess the acute effects of sleep disruption on clinically relevant cardiac ectopy pertinent to atrial fibrillation (AF).				
SPECIFIC OBJECTIVES	 Primary: To assess the effect of sleep disruption on daily number of cardiac ectopic beats. Secondary: To assess the effect of sleep disruption on daily number of premature atrial contractions (PACs). To assess the effect of sleep disruption on daily number of premature ventricular contractions (PVCs). To assess the effect of sleep disruption on daily number of AF episodes. 				
NUMBER OF PARTICIPANTS	100				
PARTICIPANT SELECTION CRITERIA	 Inclusion Criteria: Age 21 years or older Have a hypoglossal nerve stimulation (HGNS) device implanted for obstructive sleep apnea and followed up at UCSF Are willing to abstain from using the HGNS device for no more than two consecutive days as instructed over the 14-day trial period Able and willing to provide written informed consent Exclusion Criteria: Currently pregnant or trying to get pregnant Are currently taking Class 1 or 3 anti-arrhythmic medications Have a history of permanent AF or expected to have AF throughout the study period 				

Version #: 1.1 Version Date: 03 June 2025 Page 6 of 21

	 Have congenital heart disease Are >40% ventricular paced Are unable to read or sign to provide informed consent 				
STUDY DURATION	Participants will participate for approximately 2 weeks. • Randomization and monitoring: up to 2 weeks.				
PROCEDURE	After being fitted with an automatically recording electrocardiographic monitor, the HGNS device will then be "on" versus "off" (where "off" is turning off the HGNS device for one night and "on" is turning on the HGNS device) over the ensuing 14 days. Participants will be randomized to "off-on" versus "on-off" periods, assuring no more than two consecutive days of either device use or not. Electrocardiographic monitoring data will be used to assess for endpoints.				
PRIMARY ENDPOINT	The daily number of cardiac ectopic beats				
SECONDARY ENDPOINTS	 The daily number of PACs The daily number of PVCs The daily presence versus absence of AF episodes ≥ 30 seconds 				
STATISTICS Primary Analysis Plan	Our primary analyses will employ intention-to-treat principles, examining randomization assignment as the primary predictor.				
Rationale for Number of Participants	Using a two-tailed alpha of 0.05, we estimate we will need 100 participants to have 80% power in intention-to-treat analyses comparing nights on and off HGNS to detect a 2% increase in cardiac ectopy.				

Version #: 1.1 Version Date: 03 June 2025 Page 7 of 21

1 INTRODUCTION

1.1 BACKGROUND

Sleep disorders and poor sleep are a major public health problem owing to their prevalence and adverse effects. One health condition that sleep disorders have long been implicated in is the development of AF. AF is the most common sustained cardiac arrhythmia. In a recent study, we estimated that the current US national prevalence of diagnosed AF is at least 10.55 million, comprising 4.48% of the adult population, substantially exceeding prior projections. AF is a leading cause of stroke, reduces quality of life, increases risks of myocardial infarction and dementia, and results in > \$28 billion in US healthcare expenditures annually.

The relationship between poor sleep and incident AF was initially attributed to a common association with obstructive sleep apnea (OSA). However, emerging evidence suggests that chronic sleep disruption independent of OSA may play a role in the development of AF. Indeed, work largely from our group has revealed that abnormal sleep characteristics including frequent nighttime awakening, less rapid eye movement (REM) sleep, and a diagnosis of insomnia may predict incident AF, even after adjustment for OSA.^{4,5} Furthermore, studies of the circadian variation of arrhythmia onset patterns in patients with AF have shown a nocturnal predominance, suggesting that nocturnal events such a disrupted sleep may be arrhythmogenic.^{6,7} Whereas the available evidence mostly support chronic sleep disruption as a risk factor for incident AF, less is known about the near-term risk of a discrete AF episode following a night of disrupted or poor-quality sleep.

1.2 SIGNIFICANCE

Acute lack of sleep has been identified by patients as one of the most common triggers of AF.⁸ In the Individualized Studies of Triggers of Paroxysmal Atrial Fibrillation (I-STOP-AFib) randomized clinical trial conducted by our group, poor sleep was associated with an immediately increased risk for self-reported AF episodes, and a dose-response relationship existed such that progressively worse sleep was associated with longer episodes of AF the next day.⁹ These data suggest that sleep quality may be a potentially modifiable, immediate, trigger of AF. However, in this study, both sleep quality and AF episodes were subjectively assessed based on self-report, highlighting the need for studies of the relationship of poor sleep and AF episodes using objective measurements.

Given evidence regarding chronic effects of sleep disruption, why is it important to study acute effects as proposed here? There are several reasons. First, while long-term risk factors for AF have been well-established, there is growing interest among both patients and expert clinicians and investigators that understanding acute triggers of AF are important.^{8, 10, 11} Second, patient behavior is generally more strongly motivated or changed at the prospect of immediate rather than delayed effects.^{12, 13} Third, the study of such acute effects may provide more precision and more compelling data regarding causal effects—for example, randomized trials of sleep apnea treatment of AF have thus far failed to demonstrate meaningful chronic effects.^{14, 15} Of note, those studies relied on

external machines to treat sleep apnea, devices that are notoriously unwieldly and subject to poor patient compliance.

This will be the first randomized case-crossover assessment to reveal immediate relationships between sleep disruption and more frequent clinically relevant common cardiac arrhythmias pertinent to and potentially including AF episodes. Specifically, premature atrial contractions (PACs) are the most potent predictor of AF. ¹⁶⁻¹⁸ Other potentially important arrhythmias are premature ventricular contractions (PVCs), a higher frequency of which is clinically relevant as it predicts future heart failure. ^{19, 20} Because everyone experiences PACs and PVCs, use of continuously worn ECG monitors that quantify such common ectopy can be used to harness sufficient power to evaluate clinically relevant outcomes as done in the Coffee and Real-time Atrial and Ventricular Ectopy (CRAVE) study. ²¹

Compelling evidence of the direct impact of sleep disruption on discrete AF episodes would be directly and immediately relevant to clinical care of our patients. In fact, identifying near-term triggers of AF is a high priority for patients with AF and may effectively determine lifestyle modifications that can meaningfully affect the risk of an arrhythmia occurrence. 8, 10, 22

2 STUDY OBJECTIVES

2.1 General Objective

This randomized case-crossover trial aimed to test the hypothesis that sleep disruption acutely increases clinically relevant cardiac ectopy pertinent to AF, specifically the frequency of PACs and PVCs.

2.2 Specific Objectives

- Primary:
 - To assess the effect of sleep disruption on daily number of cardiac ectopic beats.
- Secondary:
 - o To assess the effect of sleep disruption on daily number of PACs.
 - o To assess the effect of sleep disruption on daily number of PVCs.
 - To assess the effect of sleep disruption on the daily presence versus absence of AF.

3 STUDY DESIGN

3.1 Study Overview

This is a single center, non-blinded, prospective, randomized, case-crossover trial, where 100 participants will be randomized to turning "on" or "off" their hypoglossal nerve stimulation (HGNS) device each day of a 14-day monitoring period. Participants will wear an automatically recording electrocardiographic (ECG) monitor and utilize a text messaging software for surveys and data capture. Participants will also share their sleep information from their HGNS device with the investigators.

4 CRITERIA FOR EVALUATION

4.1 Primary Endpoint

The daily number of ectopic beats (per 24-hour period).

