5 PARTICIPANT SELECTION

5.1 Inclusion Criteria

Participants must meet all the following to be eligible:

- Are age 21 years or older
- Have a HGNS device implanted for OSA and followed up at UCSF
- Are willing to abstain from using the upper airway stimulation device for no more than two consecutive days as instructed over the 14-day trial period
- Able and willing to provide written informed consent

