5.2 Exclusion Criteria

- Currently pregnant or trying to get pregnant
- Are currently taking class 1 or 3 anti-arrhythmic medications
- Have congenital heart disease
- Ventricular pacing >40%
- Are unable to read or sign to provide informed consent

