10.2 Statistical Analysis Plan (SAP) and Outcome Assessment

Our primary analyses will employ intention-to-treat principles, examining randomization assignment as the primary predictor. Secondary analyses will examine "per-protocol" compliance, which will also allow for quantitative assessments of outcomes per the number of hours off hypoglossal stimulation as the predictor. We will employ logistic regression with robust standard errors (to take clustering within individuals into account) for the dichotomous presence or absence of outcomes (such as at least one daily PAC, PVC, or episode of AF), and a negative binomial model to assess number of daily events.

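### The 24-hour ectopy and PAC counts take no account of time in AF, so any lengthening of AF on off days would attenuate the PAC part of the contrast by an unknown amount

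*Protocol*

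**What the plan says.** The primary endpoint in Protocol section 4.1 is "The daily number of ectopic beats (per 24-hour period"). Section 4.2 adds daily PAC and PVC counts as secondary endpoints. Section 2.1 states the hypothesis for ectopy, "specifically the frequency of PACs and PVCs", so the primary count contains both kinds of beat. Section 10.2 provides "a negative binomial model to assess number of daily events", with randomised assignment as the primary predictor; it mentions no exposure time or offset.

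AF enters only as a separate secondary endpoint, which the synopsis words as "The daily presence versus absence of AF episodes ≥ 30 seconds". Nothing connects it to the ectopy count.

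On eligibility, the synopsis excludes people who "Have a history of permanent AF or expected to have AF throughout the study period". Section 5.2 has no AF item. Paroxysmal AF is therefore eligible under either list. Participants are selected for an implant ("Have a HGNS device implanted for OSA and followed up at UCSF"), not for AF.

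**The concern.** A PAC can be registered only while the atria are not fibrillating, so hours in AF add nothing to the PAC count. Section 1.2 allows that sleep disruption may affect AF episodes as well as ectopy, and section 2.2 makes AF a secondary objective. If nights off HGNS lengthen AF, off days hold fewer hours in which a PAC can be counted. The loss then depends on assignment and runs against the hypothesised increase. It would fall on AF-prone participants, who may have more PACs than average: section 1.2 says that "premature atrial contractions (PACs) are the most potent predictor of AF".

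The target effect is small. Section 10.1 sizes the trial for a 2% increase, and 2% of 24 hours is 0.02 × 1440 = 28.8 minutes. A modest average difference in AF time could thus be of the same order as the effect sought. A weak or null ectopy result could not then be told apart from PACs displaced by AF.

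**Working it through.** **The plan's own figure.** Section 10.1 gives 100 participants, two-sided alpha 0.05, 80% power and a 2% increase. It gives no mean count, SD, dispersion or within-person correlation, so the 100 cannot be reproduced. Back-solving with a paired normal approximation on the log ratio gives the SD of the per-participant mean log ratio that would make it true:

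SD = ln(1.02) × √100 / (1.960 + 0.842) = 0.0707.

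**Effect of AF time on the count.** Let s be the share of ectopy carried by AF-prone participants, q the PAC share of ectopy, and h_on and h_off their daily AF hours. The true increase is 2% per hour outside AF, and PVCs are counted throughout. A negative binomial model with assignment as the only predictor estimates the ratio of mean counts, so shares are weighted by count:

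observed ratio = 1.02 × (24 − s·q·h_off) / (24 − s·q·h_on).

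The protocol gives none of s, q, h_on or h_off. All values below are assumptions.

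| s | h_on / h_off | q = 1 (all PACs) | q = 0.5 |
|---|---|---|---|
| 0.05 | 1 / 2 | 1.02 × 23.90/23.95: +1.79% | 1.02 × 23.95/23.975: +1.89% |
| 0.15 | 2 / 4 | 1.02 × 23.40/23.70: +0.71% | 1.02 × 23.70/23.85: +1.36% |
| 0.15 | 1 / 4 | 1.02 × 23.40/23.85: +0.08% | 1.02 × 23.70/23.925: +1.04% |
| 0.25 | 2 / 4 | 1.02 × 23.00/23.50: −0.17% | 1.02 × 23.50/23.75: +0.93% |
| 0.25 | 1 / 4 | 1.02 × 23.00/23.75: −1.22% | 1.02 × 23.50/23.875: +0.40% |

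**Break-even.** Take no AF on on-days and h extra AF hours per off day. The true 2% is cancelled when 1.02 × (1 − s·q·h/24) = 1, that is, when s·q·h = 24 × (1 − 1/1.02) = 0.471 h. Averaged over all ectopy-weighted off days (s = 1), this is 28 minutes if all ectopy is PACs, 38 at 75%, 56 at 50% and 113 at 25%.

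If only AF-prone participants have the extra AF, the hours needed in them per off day are:

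| s | q = 1 | q = 0.5 |
|---|---|---|
| 4.48% | 10.5 h | 21.0 h |
| 20% | 2.4 h | 4.7 h |
| 50% | 0.94 h | 1.9 h |

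The 4.48% is the general-adult AF prevalence in section 1.1, the only AF frequency in the document. Using it for s assumes that AF-prone participants have average ectopy.

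**Power to show an increase**, if the back-solved SD holds: Φ(ln(ratio)/0.00707 − 1.96), where 0.00707 = 0.0707/√100.

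- s = 4.48%, q = 1, h = 1: ratio 1.018, power 72%. With h = 4: ratio 1.012, power 41%.
- s = 20%, h = 1: ratio 1.0115, power 37% if q = 1; ratio 1.016, power 60% if q = 0.5.
- s = 4.48%, h = 30 seconds, the synopsis threshold for an AF episode: ratio 1.020, power 80%, that is, no visible change.

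**The case against.** A reader might infer that off nights which provoke AF will hide or reverse the ectopy effect. The documents do not support that.

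- The primary count includes PVCs. None of the five scenarios reverses when half the ectopy is PACs.
- Participants are not selected for AF, and users of class 1 or 3 anti-arrhythmic drugs are excluded. At 4.48% and average ectopy, cancellation needs more than 10 extra AF hours per off day.
- The stated hypothesis concerns PACs and PVCs. An AF effect is a secondary question.
- If PACs also rise by more than 2% outside episodes in AF-prone participants, their counts need not fall.

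All of this stands, and it limits the size of the problem. It does not remove it: 4.48% is not a figure for this OSA population, average ectopy in AF-prone participants is doubtful given section 1.2, and the secondary PAC count gets no relief from PVCs.

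An AF effect would also not go unseen, because AF has its own endpoint. That endpoint is yes or no per day, however, so it cannot show how many PAC-eligible hours were lost.

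A further tempting step is to replace the primary endpoint with a rate outside AF. Total daily ectopy by assignment is a legitimate intention-to-treat quantity. Non-AF time arises after randomisation, and dropping nights with no non-AF time would remove randomised nights according to their outcome.

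Lastly, nothing links lost patch time to assignment, so it is not part of this bias. The protocol does not say how unrecorded hours are scored, and a separate SAP, not available here, may cover it.

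**Conclusion.** The point holds as a risk of attenuation of unknown size. The endpoints are raw 24-hour counts with no stated exposure time, paroxysmal AF is eligible, and longer AF on off days would pull the PAC part of the contrast toward no effect. Under the assumed shares and hours, a true +2% would be observed as anything from +1.8% to −1.2% if all ectopy is PACs, and from +1.9% to +0.4% if half is. Cancellation or reversal is the extreme case: it needs hours of extra AF in participants carrying a large share of the ectopy. These figures rest on assumed AF hours, ectopy shares and PAC share, on a uniform 2% rise outside AF, and on full PVC detection in AF. The power figures also rest on the back-solved SD. The issue merits a prespecified supporting analysis, not a new primary endpoint.

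**What to change.** 1. In section 10.2, add the log of analysable recorded hours as an offset in the negative binomial models for total ectopy, PACs and PVCs. Section 8.1 expects that sensors may be moved or not worn, and Appendix 1 lets monitoring end with tolerance; the offset ensures that unrecorded time is not scored as ectopy-free. It does not correct for AF, because AF time is recorded time.
2. Keep total daily ectopy by assignment as the primary intention-to-treat quantity, with all randomised nights, including those with AF.
3. Prespecify a sensitivity analysis of PACs per analysable non-AF hour (offset: log non-AF hours), with PVCs per analysable hour.
4. Report AF hours by assignment beside the primary result, so that a null or reversed ectopy contrast can be told apart from displacement by AF.
5. Reconcile the AF exclusion in the synopsis with section 5.2, which omits it.

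The cost is wording and a few extra analyses. Section 7.3 says that the monitor records every heartbeat, so no new data collection is needed. The drawback is that non-AF time is post-randomisation, so the analysis in item 3 supports the primary and does not replace it.

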8 RISK AND BENEFIT ASSESSMENT

8.1 Risks

Potential risks of the study include the following:

- *Small risk of loss of privacy*: Data that the participant provides to the study may be sensitive and could be embarrassing to participants or lead to insurance coverage problems if it were leaked (e.g., obesity or very high blood pressure).
- *Financial risk*: Participating in the study may make participants want to access the healthcare system more often or purchase health-related devices to link to the study, and that all costs money.
- *Risks of study sensors*: Allergy to the adhesive used for the event monitor electrodes can lead to a rash, pruritus, and/ or painful irritation. Topical steroids will be provided if needed and participants will be provided an option to decline if they are concerned given past experience. As with previous studies, sensors may be moved and/ or not worn if irritation is not tolerable (in which case, late screenfailures and alternative/ additional participants may be used for replacement).
- Risks of HGNS withdrawal: as expected participants may experience an increase in sleep disruption on the days their device is off, potentially leading to a relapse of their OSA symptoms. There should be no long-term effects of therapy withdrawal. Indeed, a previous study showed that 1-week continuous withdrawal of therapeutic HGNS results in acute worsening of both objective and subjective measures of sleep and breathing, but with return of the positive therapeutic effects upon resuming therapy. To limit the acute negative impact of the withdrawal therapy on their well-being, no participant will be instructed to turn off their device more than 7 out of the 14 participation days. It is also part of standard of care

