10 STATISTICAL METHODS AND CONSIDERATIONS

10.1 Sample Size and Randomization

Based on the frequencies that cardiac ectopy observed among 100 healthy individuals during a study examining acute effects on and off coffee, we estimate that, using a two-tailed alpha of 0.05, we will have 80% power in intention-to-treat analyses comparing nights on and off HGNS to detect a 2% increase in cardiac ectopy—meaning, we believe 100 participants will provide adequate power to test our hypothesis.

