APPENDIX 1. SCHEDULE OF EVENTS

	PRE-SCREENING (Pre-Consent)	BASELINE VISIT (Before Day 1)	DEVICE FITTING VISIT (Day 1)	MONITORING (Day 1-15 ^b)	MONITORING CLOSE-OUT VISIT (Day 15 ^b)
Eligibility Review	X				
Informed Consent		X			
Demographics		X			
Medical Conditions		X			
Medications		X			
Baseline Alcohol Consumption		X			
Smoking History		X			
Arrhythmia History		X			
Baseline sleep surveys		X			
Mobile apps download and set up			X		
ECG monitor application			X		
Randomization				X	
Daily sleep surveys				X	
Home Sleep Apnea Test				X	
Monitor return					X
Randomization Compliance Survey					X

^a These activities will only be completed if a participant is willing and able (and are therefore considered "optional")

Version #2.0: Version Date: 07 May 2025 Page 21 of 21

^b 15 days or for as long as a participant is tolerant of study monitors (whichever occurs first)

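### The daily ectopy count has no stated link to recorded ECG hours although incomplete patch wear is foreseen, so partly recorded days may add avoidable noise against a 2% target

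*Protocol*

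**What the plan says.** Section 4.1 defines the primary endpoint as "The daily number of ectopic beats (per 24-hour period". Section 4.2 lists daily PACs, daily PVCs and daily presence of AF. Section 10.2, whose title includes the SAP, takes randomised assignment as the primary predictor and uses "a negative binomial model to assess number of daily events". Neither section mentions recorded or analysable hours, an exposure term, or a minimum wear time.

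Section 7.8 asks for continuous wear on Days 1 to 14, but other places expect less:
- Section 8.1: "sensors may be moved and/ or not worn if irritation is not tolerable".
- Appendix 1, footnote b: monitoring lasts "15 days or for as long as a participant is tolerant of study monitors (whichever occurs first".
- Section 6.2 anticipates truncated follow-up and answers it only by keeping on and off days balanced.

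The time of monitor application is given twice and differently. Section 7.7 has the devices fitted at the Baseline Visit, before Day 1. Appendix 1 puts ECG application at a separate fitting visit on Day 1.

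On power, 10.1 states that, "using a two-tailed alpha of 0.05, we will have 80% power in intention-to-treat analyses", the trial is able "to detect a 2% increase in cardiac ectopy" with 100 participants.

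**The concern.** Ectopic beats can be counted only while the patch records. If a partly recorded day is entered as a complete day, its count is too low by roughly the unrecorded fraction, for reasons unrelated to the heart or the device assignment. Each such day falls on one side of an off/on pair and moves that participant's contrast by several percent, while the target effect is 2%. Reported daily ectopy is also lowered, and a day could be scored free of AF on the strength of part of the day only. The recorded time needed to prevent this is available, because the monitor records every heartbeat (7.3).

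**Working it through.** **Inputs from the protocol.** 100 participants; two-sided alpha 0.05; 80% power; 2% increase, read as relative (10.1). Days are randomised in off/on pairs, giving 7 off and 7 on days per participant over 14 days (7.8).

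**Inputs the protocol does not give.** The mean, dispersion and within-person variation of daily counts; 10.1 says only "Based on the frequencies that cardiac ectopy observed among 100 healthy individuals". The share of partial days and the fraction recorded on them are also absent. These are assumptions below.

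**The plan's own figure.** The 80% cannot be reproduced without a variance, so the variance was back-solved.
- Required standard error: 2 / (1.960 + 0.842) = 0.714 percentage points. On the log scale, ln(1.02) = 0.0198 gives 0.707, practically the same.
- Per-participant SD of the contrast: 0.714 × √100 = 7.14 points.
- Within-person day-to-day SD: 7.14 × √(7/2) = 13.4%, or about 0.132 on the log scale.

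**Effect of one partial day.** With a fraction f recorded, that day is understated by 1 − f: 50% at 12 of 24 hours, 75% at 6 hours. The participant's mean daily count over 14 days falls by 0.5/14 = 3.6% at f = 0.5. The off/on contrast moves by ±(1 − f)/7 = ±0.5/7 = ±7.1%. The sign follows the randomised order, so the average shift is zero.

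**Effect on power.** If a share p of participants has one half-recorded day, the added SE is √p × 7.14/√100, the total SE is √(0.714² + added²), and power is Φ(2/total − 1.960).

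| p (assumed) | Added SE | Total SE | Power |
|---|---|---|---|
| 0% | 0 | 0.714 | 80% |
| 10% | 0.23 | 0.749 | 76% |
| 25% | 0.36 | 0.798 | 71% |
| 50% | 0.51 | 0.874 | 63% |

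A simulation of 4,000 runs at the same SD gave 74%, 68% and 61% for the last three rows. With recorded hours in the denominator it gave 78% to 80%.

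**A different assumed pattern.** Let each day be partial with a fixed probability and the recorded fraction be uniform between 0 and 1. Simulated power (2,000 runs each, SD 0.132) was about 67%, 52% and 39% when 2%, 5% and 10% of days were partial. With recorded hours as exposure it was about 81%, 80% and 78%. The mean log ratio stayed near 0.02 with and without the exposure term, which confirms that the contrast is not biased when partial wear is unrelated to assignment.

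**Sensitivity to the variance.** At a daily SD of 0.3 the SE with full recording is 0.3 × √(2/7)/√100 = 1.604 points and power is Φ(1.980/1.604 − 1.960) = 23%. Adding 0.51 gives a total SE of 1.68 and power of 22%. In the second pattern with 10% partial days, power at this SD was about 18% without the exposure term and 23% with it. At an SD of 0.5 or more, power was about 11% or less throughout and the term hardly mattered.

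**The case against.** The strongest objection is that nothing here is stated wrongly. Section 10.2 names a model family in half a sentence and excludes no exposure term. An offset or a valid-day rule may sit in a separate SAP that was not available, and a count per 24 hours can be read as a rate scaled to 24 hours. This stands to the extent that one may not say the trial will ignore recorded hours, or that short days will be scored free of AF; a reader might infer both, but only from silence. What remains is that the definition of the primary endpoint belongs in the protocol, and the present wording permits two readings that give different data whenever recording is partial.

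A second objection is that partial days may be rare. Section 8.1 allows replacement when a sensor is not tolerated, 9.3 replaces participants who withdraw, and stopping monitoring early gives missing days plus at most one truncated day. That is fair, and the protocol gives no frequency.

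Third, the back-solved variance leaves no slack, so any added noise must take power below 80%. The healthy-volunteer counts behind 10.1 may also already contain wear variation. Both points stand and limit the figures to an illustration.

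A reader might also take Appendix 1 to mean that everyone loses half of Day 1, which in the same formula gives 51% power. The documents do not support this. Section 7.7 says otherwise, the appendix page carries a different version and date (2.0, 07 May 2025) from the body (1.1, 03 June 2025), and no section fixes when the 24-hour count begins.

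**Conclusion.** The point holds as a gap in how the primary endpoint is fixed, worth correcting before data are seen. As worded, the count and its model carry no stated adjustment for recorded time, while the protocol expects recording to be incomplete. The harm is added variance and understated ectopy on the affected days. A reader might infer a biased treatment effect; randomisation within pairs rules that out as long as loss of recording is unrelated to assignment, and nothing in the protocol suggests otherwise.

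The size is conditional. Power of about 76% to 63% applies if 10% to 50% of participants have one half-recorded day and the daily SD is about 13%, the value that makes the stated 80% true. Neither assumption can be checked from the protocol. If the SD is 0.3 or more, power for a 2% effect is already far below 80% with complete recording, and partial days are a minor part of the problem.

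**What to change.** - In 4.1 and 4.2, define total ectopy, PAC and PVC counts relative to analysable recorded ECG hours within each assigned 24-hour period.
- In 10.2, add log(recorded hours) as an offset in the negative binomial model.
- For the daily AF endpoint, pre-set a minimum recorded time below which a day without detected AF is set to missing and not scored as absent.
- Reconcile 7.7 and Appendix 1 on when the monitor is applied.

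An offset assumes that the recorded hours represent the whole day. Section 1.1 cites circadian variation of arrhythmia onset, and the simulations included none, so they may flatter the offset. Comparing only the clock hours recorded on both days of a pair, or omitting pairs with an unrecorded night, could address this, but at most as a sensitivity analysis: 10.3 commits the main ITT analysis to the data collected from all randomised participants.

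The cost is protocol wording and minor programming. The small downside is that a minimum-hours figure must be fixed in advance and a few AF days become missing.
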